### **Description of demographic and clinical characteristics among patients with mRCC treated with 2L sunitinib therapy following 1L IO therapy**

Baseline demographic and clinical characteristics prior to or on the index date will be described using the mean (standard deviation [SD]) and median (interquartile range [IQR]) values for continuous variables and frequency distributions for categorical variables.

### **Characterization of clinical outcomes among patients with mRCC treated with 2L sunitinib therapy following 1L IO therapy**

The clinical outcomes will be analyzed as follows:

- OS and TTD will be analyzed using Kaplan-Meier estimator;
- Reasons for 1L IO and 2L sunitinib therapy discontinuation will be described using relative frequencies;
- Physician-assessed best tumor response (ie, ORR, stable disease, and progressive disease) to 2L sunitinib therapy will be described using relative frequencies.

Stratification by IMDC prognostic risk groups (ie, favorable, intermediate, and poor) may be performed pending on sample size. One interim analysis will be performed to examine sufficiency of sample size and duration of follow-up.

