## 7. RESEARCH METHODS

### 7.1. Study Design

This is a retrospective, longitudinal cohort study that involves the analysis of retrospective data collected through the IMDC database for selected academic clinical sites participating in this study (detail on clinical sites is provided in [Section 7.4](#)). A cohort of patients treated with sunitinib as the 2L therapy after treatment with IO agents as 1L therapy will be assessed.

The *index date* will be defined as the date of initiation of 2L sunitinib therapy. The *baseline period* will be defined as the time from mRCC diagnosis to the index date. The *follow-up period* will be defined as the time from the index date to the earliest of death or end of data availability. Figure 1 depicts the study design scheme.

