### Outcomes

- OS, defined as the time between initiation of 2L sunitinib therapy and death.
- TTD, defined as the time between initiation of 2L sunitinib therapy and discontinuation of therapy for any reason including progression, death, and toxicity.
  - TTD for 1L IO (ie, time between initiation of 1L IO and discontinuation of therapy for any reason).
- Time to initiation of 2L sunitinib from discontinuation of 1L IO.
- Reasons for treatment discontinuation in 1L IO and 2L due to:
  - Disease progression;
  - Toxicity;

- Death;
- Other reasons.
- Physician-assessed best response in 2L while being treated with sunitinib, defined as the objective response rate (ORR) (sum of partial response and complete response), progressive disease, and stable disease.

Covariates (assessed during the baseline period or on index date)

- Gender;
- Age at time of 2L sunitinib initiation;
- Race **CCI**;
- Date of mRCC diagnosis;
- Prior nephrectomy status;
- **CCI**.
- Histology type:
  - Non-clear cell RCC;
  - Clear cell RCC.
- Number of metastatic sites (eg, 1 site or more than 1 site).
- Site of metastases (eg, brain metastasis, bone metastasis).
- IMDC prognostic risk factors:
  - Time from RCC diagnosis to systemic treatment initiation <1 year.
  - Karnofsky performance status (KPS) <80%.
  - Hemoglobin <lower limit of normal (LLN).
  - Serum corrected calcium >upper limit of normal (ULN).
  - Neutrophil count >ULN.
  - Platelet count >ULN.

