#### 7.5. Study Size

The IMDC database has 73 patients who received 1L IO and 2L sunitinib. Power calculations were not performed as the objectives were descriptive.

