#### 7.7. Data Analysis

##### Identification of study cohort

The study population of interest in this study are patients with mRCC treated with 2L sunitinib therapy following 1L IO therapy whereby the earliest date of 2L sunitinib initiation was April 15, 2014. Each patient's eligibility for this study will be verified against the eligibility criteria.

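### Reasons for stopping 2L sunitinib are to be given as crude relative frequencies with no denominator and no place for patients still on treatment, so the reported split may depend on the date of the data cut.

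*Combined protocol and SAP*

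**What the plan says.** Reasons for treatment discontinuation are a named clinical outcome in section 6. Section 7.3 introduces them with "Reasons for treatment discontinuation in 1L IO and 2L due to" and lists four: disease progression, toxicity, death and other. There is no category for treatment still ongoing.

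Section 7.7 handles the event and its reasons differently. For the event, "OS and TTD will be analyzed using Kaplan-Meier estimator". For the reasons, "Reasons for 1L IO and 2L sunitinib therapy discontinuation will be described using relative frequencies". The two describe the same occurrence, since section 7.3 defines the TTD endpoint as ending at "discontinuation of therapy for any reason including progression, death, and toxicity".

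Follow-up runs from the start of 2L sunitinib to the "earliest of death or end of data availability" (section 7.1). Section 7.7 says that "the earliest date of 2L sunitinib initiation was April 15, 2014", and section 4 puts the end of data collection in November 2019. No latest start date, minimum follow-up or exclusion criterion is set. On size, "The IMDC database has 73 patients who received 1L IO and 2L sunitinib" (section 7.5). Section 7.7 also plans one interim look at whether sample size and follow-up are sufficient, but attaches no rule to the analysis of reasons. The limitations in section 7.8 do not mention patients still on treatment.

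**The concern.** A patient still on sunitinib at the data cut has no reason for stopping yet. Kaplan-Meier allows for such patients when estimating time to stopping; a plain percentage of reasons does not. Two denominators are open to the analyst, and each has a defect if the result is read as the eventual split of reasons:

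- **All 73 patients.** Every reason is understated whenever anyone is ongoing. This needs no assumption about timing.
- **Patients who have stopped.** Reasons that tend to occur early are over-weighted, because late stops are the ones not yet seen.

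In both cases the answer shifts with how recently the cohort started treatment. The balance of toxicity against progression is what a reader would use to judge tolerability of sunitinib after IO. In a purely descriptive study these percentages are themselves the result, and the denominator could be chosen after the data are seen.

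**Working it through.** **The plan's own figures.** There is nothing to reproduce. The 73 is a database count, and "Power calculations were not performed as the objectives were descriptive". The documents give no median TTD, no split of reasons, no timing of reasons and no number still on treatment. The check therefore asks how large the effect could be over stated assumptions.

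**Inputs from the documents.** N = 73. The window from 15 April 2014 to the end of November 2019 is T = 67.5 months.

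**Step 1: proportion still on sunitinib at the cut.** Assume exponential time to stopping, λ = ln 2 / median, with medians of 4 to 12 months.

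- Entry uniform over T: ongoing = (1 − e^(−λT)) / (λT).
- Entry rising linearly towards the cut: ongoing = 2/(λT) − 2(1 − e^(−λT))/(λT)².

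For a median of 6 months, λ = 0.1155 and λT = 7.80. Uniform entry gives 0.9996/7.80 = 12.8%. Rising entry gives 0.2565 − 0.0329 = 22.4%. Over the whole grid the range is 8.6% (median 4, uniform) to 38.4% (median 12, rising), or about 6 to 28 of the 73.

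**Step 2: all 73 as denominator.** The four reasons together sum to 1 − ongoing, that is 91.4% down to 61.6%.

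**Step 3: stopped patients as denominator, proportional hazards.** If toxicity is a constant 25% of the hazard, its share among stopped patients is exactly 25.0% in every scenario, so there is no bias. Over all 73 it reads 22.9% down to 15.4%.

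**Step 4: stopped patients as denominator, early toxicity.** Assume toxicity is 50% of the hazard in the first 3 months and 10% afterwards. The eventual share is 0.5(1 − e^(−3λ)) + 0.1e^(−3λ). For a median of 6 months this is 0.5 × 0.2929 + 0.1 × 0.7071 = 21.7%.

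| Median TTD, entry | Ongoing | Eventual toxicity | Among stopped | Over all 73 |
|---|---|---|---|---|
| 4 months, uniform | 8.6% | 26.2% | 27.4% | 25.0% |
| 6 months, uniform | 12.8% | 21.7% | 23.2% | 20.2% |
| 6 months, rising | 22.4% | 21.7% | 24.5% | 19.0% |
| 12 months, rising | 38.4% | 16.4% | 19.9% | 12.3% |

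The inflation among stopped patients is 1.2 to 3.5 points.

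**Step 5: a stronger timing contrast.** Assume Weibull toxicity with falling hazard (shape 0.7), Weibull progression with rising hazard (shape 1.3) and exponential other reasons including death; eventual shares of 33%, 57% and 10%; median TTD of 4.3 to 6.8 months; and entry ranging from uniform to all in the last 24 months. Then 9% to 36% are ongoing. Among stopped patients toxicity reads 34% to 39% and progression 51% to 56%. Over all patients toxicity reads 25% to 31% and progression 32% to 51%. The inflation of toxicity among stopped patients is about 1 to 6 points. At the late-entry extreme (median 6.8 months, 36% ongoing) the choice of denominator alone moves toxicity from 39% to 25%.

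**Step 6: sampling error for scale.** The 95% half-width is 1.96 × √(p(1 − p)/n). For p = 25% and n = 73 it is 9.9 points. For p = 33% it is 10.8 points at n = 73 and 13.4 points at n = 47 (about 36% ongoing).

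**Step 7: what fixed-time cumulative incidence would show.** Under the step 5 model, toxicity is 21% to 26% by 6 months and 28% to 31% by 12 months; progression is 20% to 30% and 36% to 47%. These values do not depend on the entry pattern. They are also not the eventual shares of 33% and 57%.

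**The case against.** The strongest case against has four parts.

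**Nobody is known to be ongoing.** This stands. A reader might infer from Kaplan-Meier and open follow-up that some patients certainly remain on sunitinib. The documents make that plausible but give no count, and section 7.7 is silent on such patients rather than assuming that everyone has stopped.

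**Over-statement of toxicity is assumed, not shown.** This also stands. It is tempting to say that the planned table will exaggerate toxicity. That requires toxicity stops to come earlier than the others, and no timing is given. Under proportional hazards the bias among stopped patients is zero. Where it exists, 1 to 6 points is smaller than a half-width of 10 to 13 points, though it is systematic and a confidence interval would not show it.

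**The natural denominator is patients who stopped, and a table over all 73 with an ongoing row is a correct description of status at the cut.** Largely right. The percentages mislead only if read as eventual shares. But the plan commits to neither denominator and provides no ongoing row.

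**Cumulative incidence answers a different question.** Right. In step 7, toxicity makes up 41% to 46% of stops by 6 months, further from the eventual 33% than the 34% to 39% seen among stopped patients. So it cannot be presented as recovering the eventual split, and the documents do not support calling the planned frequencies an error that must be replaced. What it does offer is a quantity that does not move with the data cut.

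The planned interim look at follow-up helps only in part, since no rule links it to this analysis.

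**Conclusion.** The point holds as a gap in specification with a better method readily available. The plan gives the composite event a method that allows for censoring and its component reasons one that does not, with neither a denominator nor a count of ongoing patients. If patients remain on sunitinib at the cut, the reported split depends on how recent the cohort is. The understatement over all 73 follows whenever anyone is ongoing; its size (reasons summing to 62% to 91%) rests on the assumed medians and entry patterns. The over-weighting among stopped patients is conditional on early timing: zero under proportional hazards, about 1 to 6 points in the early-toxicity scenarios.

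The documents do not support the firmer conclusions that patients are known to be ongoing, that toxicity will be overstated, or that relative frequencies are invalid. The point does not extend to 1L IO: every patient was selected for having moved to 2L, so relative frequencies remain adequate there. No power or alpha figure is affected.

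**What to change.** In section 7.7, for 2L sunitinib only:

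1. Keep the raw counts by reason and state the denominator for each percentage.
2. Add a row for patients still on sunitinib at the data cut.
3. Add Aalen-Johansen cumulative incidence of progression, toxicity, death and other reasons, treated as competing events, at fixed times such as 6 and 12 months with 95% confidence intervals. Censor ongoing patients at their last on-treatment date.
4. Label these estimates as the risk of stopping for each reason by the stated time, not as eventual shares.

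The cost is a sentence or two in the plan and standard software. Treatment dates and reasons are already needed for the outcomes in section 7.3. The downside is that, with 73 patients, intervals for the rarer reasons will be wide.

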**Figure 1. Study Design Scheme**

## 7.2. Setting

### 7.2.1. Inclusion Criteria

Patients will be selected based on the eligibility criteria listed below. Participation in an interventional trial for mRCC disease is allowed. Subjects will be selected irrespective of their survival status.

Patients must meet all of the following inclusion criteria to be eligible for inclusion in the study:

- Diagnosed with mRCC;
- Received IO therapy as 1L therapy;
- Received sunitinib as 2L therapy;
- Age 18 years or over at the time of mRCC diagnosis;
- Actively treated at an IMDC clinical center (to avoid incomplete data).

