#### 7.4. Data Sources

Data will be obtained retrospectively from the IMDC clinical sites.

The IMDC cohort is a multi-institutional cohort that collects data globally from international cancer centers in the United States, Canada, Denmark, Greece, South Korea, Australia, New Zealand, Japan, Singapore, Italy, and Belgium. Demographic, clinical, laboratory, and outcome data on patients with mRCC are collected retrospectively from medical charts using uniform database templates and standardized definitions to ensure data are collected consistently. Medical records include longitudinal information on patient demographic and disease characteristics, oncology-specific workups and evaluations, treatment types and duration, concurrent diagnoses as documented in physician notes, and treatment discontinuation/halt decisions.

CCI [REDACTED] will collaborate with [name] [REDACTED] from the University of Calgary. PPD [REDACTED] who will serve as the principal investigator for this study and who is also the Chair of the IMDC, to obtain data from clinical centers. The clinical centers send data to the IMDC database, and data cleaning and consolidation of the data occur twice a year.

For this proposed study, a "limited" dataset of patients treated with 1L IO therapy and 2L sunitinib therapy will be provided only. The "limited" dataset will be anonymized and will not contain any personal data. All 1L IO and 2L sunitinib patients are included in the "limited" dataset, but only a select number of variables necessary to fulfill the study objectives will be included.

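### Does the best-response outcome need a not-assessed class and a stated denominator for ORR?

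*Combined protocol and SAP*

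**What the plan says.** Section 7.3 (Outcomes) names the outcome as "Physician-assessed best response in 2L while being treated with sunitinib". The same entry then fixes its content with three classes: "defined as the objective response rate (ORR) (sum of partial response and complete response), progressive disease, and stable disease". Section 7.7 repeats the same three classes as its whole analysis plan for response: "Physician-assessed best tumor response (ie, ORR, stable disease, and progressive disease) to 2L sunitinib therapy will be described using relative frequencies". Neither place has a class for a response that was not evaluable, not assessed or not recorded, and neither names a denominator.

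The population is described more broadly. Section 7.7 (Identification of study cohort) states: "The study population of interest in this study are patients with mRCC treated with 2L sunitinib therapy following 1L IO therapy". Section 7.4 says of the limited dataset: "All 1L IO and 2L sunitinib patients are included". Section 7.2.2 lists no exclusions, and Section 7.2.1 asks for no response assessment and takes patients whether or not they are still alive. Section 7.5 counts 73 such patients in the database and explains that power was not calculated because the aims are descriptive.

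Section 7.3 also has an outcome that begins "Reasons for treatment discontinuation in 1L IO and 2L due to". It lists progression, toxicity, death and a residual class for other reasons.

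**The concern.** The response list is closed, while the cohort takes in everyone who started second-line sunitinib. A patient who stops for toxicity, death or another reason before any on-treatment assessment belongs to the cohort but to none of the three classes, unless the physician records progression. A recent starter may also have no assessment by the data cut. The discontinuation reasons have a catch-all and the response classes do not, which makes the omission look like an oversight.

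What would be at stake is the reported ORR. If some patients are unassessed, leaving them out of the denominator raises ORR. A three-row table that adds to 100% would not tell the reader whether everyone was assessed or some patients were dropped. With no stated rule, the choice could in principle be made after the data are seen.

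**Working it through.** **Inputs.** From the documents: N = 73 (Section 7.5). This count is provisional, because Section 7.6 has the most recent data transferred and Section 7.7 still has eligibility to be verified. Assumed, because the documents give neither: r responders and m unassessed patients.

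The plan states no ORR, precision or power figure, so there is nothing of its own to reproduce.

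**Step 1: ratio of the two readings.** All-treated ORR is r/N and assessed-only ORR is r/(N − m). Their ratio is N/(N − m), whatever r is:

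- m = 0: 73/73 = 1.000
- m = 1: 73/72 = 1.014
- m = 4: 73/69 = 1.058
- m = 7: 73/66 = 1.106

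**Step 2: shift in percentage points**, taken from unrounded rates.

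| Assumed r | r/73 | r/69 (m = 4) | Shift | r/66 (m = 7) | Shift |
|---|---|---|---|---|---|
| 7 | 9.6% | 10.1% | 0.6 | 10.6% | 1.0 |
| 15 | 20.5% | 21.7% | 1.2 | 22.7% | 2.2 |
| 22 | 30.1% | 31.9% | 1.7 | 33.3% | 3.2 |

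**Step 3: comparison with sampling error.** The exact (Clopper-Pearson) 95% interval for 15/73 is 12.0% to 31.6%. The shifts of 1.2 and 2.2 points for r = 15 are small against that width.

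**Step 4: a much larger m.** If 22 of 73 (30.1%) were unassessed, 51 would remain. With r = 15, ORR would be 15/51 = 29.4%, a shift of 8.9 points and still inside the interval for 15/73. With r = 20, it would be 20/51 = 39.2% against 20/73 = 27.4%. That shift of 11.8 points puts the assessed-only rate just above the upper limit of 39.1% for 20/73. Nothing in the documents suggests an m of that size.

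**Step 5: which reading the text supports.** The cohort definition, the description of the limited dataset, the absence of exclusions and the heading of the analysis ("Characterization of clinical outcomes among patients with mRCC treated with 2L sunitinib therapy following 1L IO therapy") all point to everyone treated. No section restricts ORR to assessed patients, so that reading rests on silence alone. Over all treated patients, any gap shows itself: with m = 7 the three rows add to 66/73 = 90.4%, and the analyst has to account for the other 7/73 = 9.6%.

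**The case for a change.** The strongest case for a change is that best response is a named outcome under the study objectives, and a single sentence is its whole analysis plan. The class list is closed in both places, and Annex 1 lists no stand-alone document that could supply the missing rule. The inclusion criterion "Actively treated at an IMDC clinical center (to avoid incomplete data") and the data queries in Section 7.6 can repair records, but they cannot create an assessment that was never made. If the risk-group strata are reported, the same gap weighs more: in an assumed stratum of 20, two unassessed patients give a ratio of 20/18 = 1.11. The remedy would be one sentence and one table row.

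The textual part of this stands: there is no class for a missing response and no stated denominator. The consequence is weaker. Response is the physician's assessment and no scheduled scan is required, so an early clinical decline may be recorded as progression, which would reduce the uncovered group by an unknown amount. Section 7.8 warns of varied criteria and schedules and of inconsistent assessment; it does not say that assessments are absent. The strata are conditional on sample size, and the stratum of 20 is assumed. An all-treated ORR is not free of fault either, because an unassessed patient is not a known non-responder and the rate can be too low. Showing the number without an evaluable response deals with both points, and that belongs to the layout of the results table.

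**Conclusion.** The three classes may not cover every treated patient, and the denominator is not spelled out. This is a gap that analysts fill sensibly; the plan contains no wrong rule, and no change is needed. The population text leads to all treated patients, and the ordinary way to complete that table is to add a row for patients without an evaluable response.

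The numerical effect is zero if everyone has a recorded response. With N = 73 and 4 to 7 unassessed patients it is 0.6 to 3.2 points for the assumed 7 to 22 responders. It grows if many more are unassessed, so the conclusion does not depend on the shift always being small. It rests on the text supporting one denominator, on that denominator making any shortfall visible, and on ORR being a descriptive outcome to which no test or decision is attached. The number unassessed and the responder counts are assumptions, and 73 may change once the cohort is final.

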### **Description of real-world treatment patterns among patients with mRCC treated with 2L sunitinib therapy following 1L IO therapy**

The following treatment patterns will be described:

- Median (IQR) and mean (SD) time from mRCC diagnosis to initiation of 1L IO therapy.
- Median (IQR) and mean (SD) time from initiation of 1L IO therapy to discontinuation of IO therapy.
- Median (IQR) and mean (SD) time from discontinuation of 1L IO therapy to initiation of 2L sunitinib therapy.
- Median (IQR) and mean (SD) time from initiation of 2L sunitinib to discontinuation of sunitinib.

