### 7.2.2. Exclusion Criteria

There are no exclusion criteria for this study.

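### Section 7.7 summarises second-line sunitinib duration by plain median and mean, although the same interval is analysed by Kaplan-Meier as TTD and some patients may still be on drug

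*Combined protocol and SAP*

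**What the plan says.** Section 7.3 (Outcomes) gives "TTD, defined as the time between initiation of 2L sunitinib therapy and discontinuation of therapy for any reason including progression, death, and toxicity". For the clinical outcomes, Section 7.7 states that "OS and TTD will be analyzed using Kaplan-Meier estimator". Later in Section 7.7, the fourth treatment-pattern item is "Median (IQR) and mean (SD) time from initiation of 2L sunitinib to discontinuation of sunitinib". That item mentions neither censoring nor patients still on treatment, and does not refer back to TTD.

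The other relevant provisions are:

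- Section 7.1 defines follow-up as "time from the index date to the earliest of death or end of data availability".
- Section 7.2.1 requires that second-line sunitinib was received, not that it was completed, and adds "Subjects will be selected irrespective of their survival status".
- Section 7.2.2 states "There are no exclusion criteria for this study", so there is no minimum follow-up.
- Section 7.6 asks for the most recent data.
- Section 7.5 gives the cohort: "The IMDC database has 73 patients who received 1L IO and 2L sunitinib".
- Section 7.7 gives a first index date ("the earliest date of 2L sunitinib initiation was April 15, 2014") but no last one.

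Section 6 names duration of sunitinib therapy as an example under the treatment-pattern objective.

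**The concern.** One interval is given two analyses, and only one of them can handle a patient who has not yet stopped. For such a patient the duration is known only to exceed the time observed so far. An ordinary mean and SD cannot use that information, so the analyst must either drop the patient or treat the time so far as a finished course. The plan does not say which.

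The report could then show two different medians for time on sunitinib, together with a mean that understates it, and nothing to tell the reader which figure describes the whole cohort. A reader who takes duration from the treatment-pattern table would get the shorter figure.

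**Working it through.** **Is it the same interval?** Both run from the start of second-line sunitinib to its discontinuation. TTD counts stopping for any reason, including death; the treatment-pattern item sets no different rule. The item has the same form as the three before it, and as the baseline summaries in Section 7.7, which points to ordinary descriptive statistics.

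**Can patients be ongoing?** Yes. Eligibility asks only for receipt of sunitinib, follow-up can end while a patient is on drug, and recent starters are not excluded. The other three intervals differ: by selection every patient has reached second-line sunitinib, so the end of data is not expected to cut them off.

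**How large could the bias be?** The plan has no figure to reproduce: 73 is a database count and no power calculation was made. The illustration below rests on assumptions.

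Inputs from the documents: n = 73; first index date 15 April 2014; end of data collection November 2019 (Section 4). Assumed: cut-off about 1 November 2019, so W = 66.5 months; exponential duration T with true median m = 6, 8 or 12 months; available follow-up C uniform on (g, W) and unrelated to T, where g = 0, 6 or 12 months is the gap between last entry and cut-off.

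With λ = ln 2 / m:

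- Proportion ongoing: p = P(T > C) = (e^(−λg) − e^(−λW)) / [λ(W − g)].
- Ongoing counted as complete: E[min(T, C)] = (1 − p)/λ, so the mean is low by exactly p.
- Ongoing dropped: the mean is low by λE[C e^(−λC)] / (1 − p).
- Medians were found numerically from the distributions of T given T ≤ C and of min(T, C).

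Worked case, m = 6 and g = 0: λ = 0.1155, λW = 7.68, e^(−λW) = 0.00046.

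- p = (1 − 0.00046)/7.68 = 0.130, and 73 × 0.130 = 9.5 patients.
- Dropped: λE[C e^(−λC)] = (1 − 0.00046 × 8.68)/7.68 = 0.1297, and 0.1297/0.870 = 0.149. The true mean of 8.66 months becomes 8.66 × 0.851 = 7.37.

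All nine cases, as percentage below the true value (m = 6 / 8 / 12):

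| | g = 0 | g = 6 | g = 12 |
|---|---|---|---|
| Ongoing, % | 13 / 17 / 25.5 | 7 / 11 / 20 | 4 / 7 / 15 |
| Median, dropped | 13.5 / 18 / 27 | 10 / 15 / 25 | 6 / 10 / 20 |
| Mean, dropped | 15 / 20.5 / 31 | 13 / 19 / 30 | 10 / 16 / 28 |
| Median, counted as complete | 12 / 15.5 / 22 | 0 / 4 / 11.5 | 0 / 0 / 0 |
| Mean, counted as complete | 13 / 17 / 25.5 | 7 / 11 / 20 | 4 / 7 / 15 |

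The zeros arise where every patient has been followed at least as long as the true median. Counting ongoing time as complete then leaves the median intact, but not the mean.

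**Would it show in a sample of 73?** In 10,000 simulated cohorts per case, the Kaplan-Meier median exceeded the median among those who stopped by an average of 0.8 / 1.5 / 3.3 months (g = 0), 0.6 / 1.3 / 3.1 (g = 6) and 0.3 / 0.8 / 2.5 (g = 12). The SD of the Kaplan-Meier median is about 1.0 / 1.4 / 2.1 months, so the average difference is below one SD in five of the nine cases: all three at m = 6, and m = 8 with g = 6 or 12. The direction is consistent, however. The plain median was the lower in about 94% to 95% of cohorts at m = 6 with g = 12, and in more than 99% in every other case.

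**If starts cluster late.** With follow-up assumed uniform over 0 to 24 months, 34% / 42% / 54% are ongoing and the median among those who stopped is 3.9 / 4.5 / 5.2 months, or 35% / 44% / 57% low. The documents do not state this window; it shows only how strongly the result depends on recent entry.

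**The case against.** The strongest reply is that the item, read literally, covers only patients who discontinued. That is a legitimate description, and on that reading what is missing is a label and an n, not a different estimator. This stands in part: labelling is an acceptable remedy for any plain summary that is kept. It does not settle the matter, because the item carries no such restriction and an unlabelled figure will be read as the duration for the cohort.

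The median and IQR could also be read as Kaplan-Meier quantiles. The mean and SD in the same item count against that, as does its match with the neighbouring items.

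Three points on weight stand. The listed outcome, TTD, is already analysed properly, so no outcome is lost. The study is descriptive, and duration of sunitinib is only an example under an objective. The percentages rest on assumptions and should not be quoted as this study's bias.

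The interim analysis in Section 7.7 will look at sufficiency of follow-up and may reduce the number ongoing, but it sets no rule for those who remain. The statement about survival status concerns vital status, not treatment status, and gives only weak support. The argument rests mainly on the follow-up definition and on the absence of any requirement that sunitinib has been stopped.

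**Conclusion.** The concern holds and is minor. The plan gives a plain mean and median for an interval it elsewhere treats as censored, with no rule for ongoing patients. If any patient is ongoing, and the end of data is unrelated to treatment duration, the plain mean is too low under either handling. The plain median is too low if ongoing patients are dropped, and may or may not be if their time is counted as complete.

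The size cannot be derived from the documents, which give no number ongoing, no last index date and no data cut-off. If all 73 patients have stopped, the bias is zero and the two medians agree. The Kaplan-Meier TTD is unaffected in every case.

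**What to change.** In the fourth treatment-pattern item of Section 7.7:

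- Report second-line sunitinib duration from the Kaplan-Meier TTD: median and quartiles with 95% confidence intervals, plus a restricted mean to a stated horizon if a mean is wanted.
- State the censoring rule. Patients still on sunitinib are censored at the end of their available data, meaning the last date they are known to be on sunitinib if treatment status is recorded less recently than vital status.
- Report the number still on sunitinib.
- Label any plain median or mean that is kept as limited to patients who discontinued, with its n.

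The three earlier intervals can keep their plain summaries; missing first-line dates are a separate matter, not assessed here.

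The cost is one or two sentences in Section 7.7. No new data or patients are needed, and the Kaplan-Meier analysis is already planned.
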